between the two treatment groups, assuming that the common standard deviation is 1.2 g/dL, using an ANOVA test with a 0.05 two-sided significance level.

For Ex-US Submission Primary Efficacy Endpoint

Based on a two-sided test at the $\alpha = 0.05$ level of significance, the study will have $> 95\%$ power to demonstrate a statistically significant difference between roxadustat and placebo, assuming that the proportion of subjects with a Hb response in the roxadustat group is at least 65% and the proportion of subjects with a Hb response in the placebo group is at most 25%.

During the course of this Phase 3 study, which is being conducted in parallel with other Phase 3 studies, up to 1200 subjects may be enrolled in this study to support the overall safety evaluation of roxadustat across pooled comparable studies in the Phase 3 program, using adjudicated composite safety endpoints of interest. The study will stop enrollment at the Sponsor's discretion, if:

- 1) the minimum of 450 subjects has been achieved to support the primary efficacy endpoint in this study, and
- 2) sufficient adjudicated safety events have been accumulated across the nondialysis Phase 3 program to support a pooled analysis of composite safety events across multiple studies in the same population.

Statistical Analysis

Intent-to-Treat (ITT): All randomized subjects.

Safety Population: All subjects who receive any dose of study drug.

Per Protocol Set (PPS): All randomized subjects who receive at least 12 weeks of study treatment, have valid corresponding Hb measurements, and are without major protocol violations. Full criteria to be defined in the SAP.

All primary and secondary efficacy analyses will be based on the ITT population. The PPS population will be utilized for supportive analysis of primary and secondary endpoints.

Laboratory values from the central laboratory will be used for all analyses. The baseline Hb value for efficacy analyses is defined as the mean of four central laboratory Hb values: the last three screening Hb values prior to randomization plus the predose Hb value on Day 1 of the Treatment Period. Hemoglobin values after a rescue therapy will not be excluded for the FDA primary efficacy analysis. Hemoglobin values within 6 weeks after a rescue therapy will be excluded for the Ex-US primary efficacy endpoint as well as other sensitivity efficacy analyses. The Mixed Model with

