9.2 Analysis Populations

The following analysis populations will be used for the statistical analysis:

- **Intent-to-Treat Population (ITT):** All randomized/enrolled subjects. All efficacy data will be analyzed using the ITT population.
- **Safety Population:** All subjects who took any dose of study medication will be included in the safety population. All safety data will be analyzed using the safety population.
- **Per Protocol Set (PPS):** All randomized/enrolled subjects who receive at least 12 weeks of study treatment, have valid corresponding Hb measurements, and are without major

protocol violations. The PPS population will be utilized for supportive analysis of primary and secondary endpoints. Full criteria for PPS exclusion will be specified in the SAP.

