9.5 Statistical Analysis Plan

A detailed SAP will be finalized prior to the final database lock. Any significant changes to the analyses described in this protocol will be highlighted in the SAP and the Clinical Study Report. The analytical methods for the composite safety endpoints of interest will be described in a region-specific pooled SAP to reflect the nature of the pooling of these endpoints across comparable studies in the Phase 3 program and the region-specific safety endpoints.

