5.2.4 Per Protocol Set (PPS)

All randomized/enrolled subjects who receive at least 8 weeks of study treatment, have valid corresponding Hb measurements, and are without major protocol violations. The PPS population will be utilized for supportive analysis of primary endpoints.

PPS1 is a subset of PPS subjects who are randomized/enrolled prior to Amendment 2. PPS2 is a subset of PPS subjects who are randomized/enrolled under Amendment 2 or later.

All primary and secondary efficacy analyses will be based on the ITT (for US FDA) or FAS (for EMA) population as the primary analysis set respectively. Primary and secondary analyses will be repeated using the FAS or ITT respectively as supportive sensitivity analyses. Additional efficacy analyses will use the FAS as specified in the TLF (Tables, Listings and Figures) index.

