12.3 ANALYSES OF SECONDARY EFFICACY ENDPOINTS

The secondary efficacy endpoints will be analyzed using the FAS population as the primary analysis population for superiority, and PPS the primary analysis set for non-inferiority.

Secondary endpoints will be tested using a fixed sequence approach to adjust for multiple endpoints comparing between pooled roxadustat vs. pooled placebo, unless otherwise specified. If a null hypothesis is rejected, the claim of roxadustat over placebo will be declared successful and the test will progress to the next comparison in sequence.

1. Ex-US submission only: Mean CFB in Hb averaged over 8 weeks of treatment at Weeks 28 to 36, without rescue therapy within 6 weeks prior to and during this 8-week evaluation period for the two treatment groups will be compared using an MMRM model with baseline Hb and eGFR as covariates and treatment group, visit, treatment*visit, and the other

- randomization stratification factors as fixed effects. The same strategy as that used in MMRM for primary endpoint will be used to choose variance covariance structure. Data up to visit of Week 52 will be included in the model. The estimates for difference of Hb CFB averaged over Weeks 28 to 36 between the two treatment groups will be generated from an estimate statement for Weeks 28 to 36. Superiority will be declared if the lower bound of the 2-sided 95% confidence interval of the difference between roxadustat and placebo exceeds 0. Missing values will be handled by the MMRM model.
2. Mean CFB in Hb averaged over Weeks 28 to 52 in a subgroup of subjects with baseline CRP>ULN for the two treatment groups will be compared using MI ANCOVA model with baseline Hb as a covariate and treatment group, visit, treatment*visit, and the above-mentioned stratification factors as fixed effects. Data up to visit of Week 52 will be included in the model. The estimates for difference of Hb averaged over Weeks 28 to 52 between the two treatment groups will be generated from an estimate statement from Visit Week 28 to 52. Superiority will be declared if the lower bound of the 2-sided 95% confidence interval of the difference between roxadustat and placebo exceeds 0.
 3. Proportion of subjects with Hb (averaged Weeks 28 to 36) ≥ 10 g/dL, without use of rescue therapy within 6 weeks prior to and during this 8-week evaluation period, will be compared using Cochran-Mantel-Haenszel (CMH) adjusting for the randomization stratification factors.

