10. Mean CFB in the SF-36 PF subscore averaged over Weeks 12 to 28 for the two treatment groups will be compared using an MMRM model as outlined above. A subgroup of subjects with baseline PF subscore below 50 will be analyzed as a sensitivity analysis.
11. Mean CFB in MAP averaged over Weeks 20 to 28 for the two treatment groups will be compared using an MMRM model as outlined above with a non-inferiority margin of 5.

12. Time to (and proportion of subjects with) protocol defined worsened hypertension for the pooled roxadustat vs pooled placebo will be compared using the approach in #4 above. Hazard ratio and its associated 95% CI will be computed between the roxadustat group versus pooled placebo. Non-inferiority will be declared if the upper bound of the 2-sided 95% CIs of the odds ratio does not exceed 1.3. Superiority will be declared if the upper bound of the 2-sided 95% CI of the hazard ratio does not exceed one. The incidence rate per PEY by treatment group will also be reported.

In MMRM above, due to large amount of visits to include in the model, the unstructured covariance pattern model will be applied first. If the algorithm for unstructured covariance pattern does not converge, then the heterogeneous Toeplitz structure will be used instead. If this second model also does not converge, then the (homogeneous) Toeplitz structure will be tried, and finally compound symmetry as a covariance structure to achieve convergence. If none of them converge, first order autoregressive (AR (1)) as a covariance structure will be used to achieve convergence.

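### The Per Protocol Set needs 12 weeks of treatment in the protocol but 8 in the SAP, and SAP 12.3 lets it decide non-inferiority on worsened hypertension, a role SAP 5.2.4 and the protocol give to ITT/FAS

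*Protocol*

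**What the plan says.** **Minimum duration.** The protocol states 12 weeks twice. The synopsis has "All randomized subjects who receive at least 12 weeks of study treatment, have valid corresponding Hb measurements, and are without major protocol violations", and Protocol 9.2 has "All randomized/enrolled subjects who receive at least 12 weeks of study treatment". SAP 5.2.4 has "All randomized/enrolled subjects who receive at least 8 weeks of study treatment, have valid corresponding Hb measurements, and are without major protocol violations". Apart from the number of weeks, the conditions are the same.

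**Who may change it.** The synopsis adds "Full criteria to be defined in the SAP", and Protocol 9.2 similarly leaves the full exclusion criteria to the SAP. Protocol 9.5 also promises: "Any significant changes to the analyses described in this protocol will be highlighted in the SAP and the Clinical Study Report". The SAP text under review contains no note that the duration was changed.

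**Role of the set.** SAP 12.3 uses FAS for superiority on the secondary endpoints, "and PPS the primary analysis set for non-inferiority". SAP 5.2.4 bases all primary and secondary efficacy analyses on ITT (US FDA) or FAS (EMA) and limits the PPS to supporting the primary endpoints. The synopsis and Protocol 9.4.3.2 make ITT primary for secondary endpoints and the PPS supportive.

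**The test affected.** SAP 12.3 item 12 covers time to worsened hypertension: "Non-inferiority will be declared if the upper bound of the 2-sided 95% CIs of the odds ratio does not exceed 1.3". The sentence says odds ratio, but the analysis it belongs to reports a hazard ratio, and it is read that way here. Under SAP section 12, efficacy time-to-event analyses run from the first dose.

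**The concern.** Two inconsistencies meet in one test. The documents disagree on who is in the PPS, and they disagree on whether the PPS decides anything for secondary endpoints.

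If SAP 12.3 governs, entry to the deciding set depends on what happens after time zero. A subject must stay on drug for 8 or 12 weeks to be counted, while the hypertension clock starts on Day 1. Neither definition makes an exception for a subject who stopped because of a blood-pressure event. Someone who meets the endpoint in Week 4 and stops in Week 6 disappears together with the event. An early rise in blood pressure that makes a subject stop is part of the harm this test exists to detect.

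SAP 13.1.2 itself says that differential dropout is suspected and may bias event rates. At stake is the chance of a false non-inferiority claim on hypertension.

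**Working it through.** **1. Who is removed.** SAP 5.4 counts treatment duration as last dose date minus first dose date plus 1. The cut-offs are therefore 8 × 7 = 56 days and 12 × 7 = 84 days.

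| Drug stopped | Protocol PPS | SAP PPS | ITT/FAS |
|---|---|---|---|
| Before Week 8 | out | out | in* |
| Week 8 to before Week 12 | out | in | in* |
| Week 12 or later | in† | in† | in* |

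*FAS also needs one dose, a baseline and one post-dose Hb. †If the other PPS criteria are met.

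A subject who has the event and stays on drug past the cut-off is not removed by the duration rule.

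**2. Size of the bias, by simulation.** The documents give no hypertension rate, dropout rate or proportion stopping after an event, so all inputs here are assumptions: placebo event rate 15% per year, background discontinuation 30% per year, one-year horizon, roxadustat hazard multiplied in Weeks 0–12 and equal afterwards, 50% of subjects with an event stopping two weeks later in both arms, 2:1 allocation, and censoring 7 days after stopping.

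| Early hazard | All subjects | 8-week PPS | 12-week PPS |
|---|---|---|---|
| Equal | 1.00 | 1.00 | 1.00 |
| Doubled | 1.27 | 1.22 | 1.18 |
| Tripled | 1.55 | 1.43 | 1.35 |

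Independent re-runs agree to about 0.02.

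**3. Expected-count check by hand.** Simpler assumptions: 800 vs 400 subjects, 52 weeks, no background dropout, placebo incidence 15%, early hazard doubled, and half of those with an event before the cut-off excluded.

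- Weekly placebo hazard: −ln(0.85)/52 = 0.003125.
- Events over 52 weeks: roxadustat 800 × (1 − exp(−0.003125 × (2 × 12 + 40))) = 145.0; placebo 400 × 0.15 = 60.0.
- Events before Week 12: 57.8 and 14.7. Before Week 8: 39.0 and 9.9.
- All subjects: (145.0/37,156 person-weeks) ÷ (60.0/19,198) = 1.25.
- 8-week set: (125.5/37,078) ÷ (55.1/19,178) = 1.18.
- 12-week set: (116.1/36,984) ÷ (52.6/19,154) = 1.14.

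Upper bounds, from HR × exp(1.96 × √(1/e₁ + 1/e₀)), are 1.69, 1.62 and 1.58. All exceed 1.3.

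**4. Would the decision change?** Non-inferiority is judged on the upper 95% bound. At 2:1 the standard error of the log hazard ratio is about √(4.5/d) for d events, so an observed HR passes only if d ≥ 4.5 × (1.96/ln(1.3/HR))².

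- HR 1.18: 4.5 × (1.96/0.0969)² ≈ 1,840 events.
- If all 1,200 subjects had an event, the observed HR would have to be below 1.3 × exp(−1.96 × √(4.5/1,200)) ≈ 1.15.

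No value in the doubled and tripled rows of step 2 passes, in any of the three sets.

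**5. The extreme case.** Same method as step 3, with placebo incidence 30%, early HR 1.5, and every subject with an early event stopping before Week 12. The result moves from 1.13 (upper bound 1.41) to 1.00 (1.29) under the 12-week rule. Under the 8-week rule, with all early events stopping before Week 8, it is 1.05 (1.34). If only half stop, the bounds are 1.38 (8 weeks) and 1.36 (12 weeks).

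**The case against.** **The SAP may set the PPS criteria.** The protocol hands the full criteria to the SAP, so 8 weeks could be the intended rule. That is a fair reading, and 8 weeks is the less biasing of the two. But the protocol states 12 weeks itself, and Protocol 9.5 asks for significant changes to be highlighted. The mismatch stands.

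**The PPS may not decide anything.** SAP 5.2.4 and the protocol point to ITT/FAS. If they govern, the bias never reaches the non-inferiority decision. This is correct, and it is why the point is conditional on SAP 12.3. A reader might infer that the SAP unambiguously decides non-inferiority on the PPS; it does not.

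**Early stopping after a blood-pressure event is assumed.** Protocol 5.3 lists no blood-pressure stopping rule, though it allows withdrawal by investigator decision, and Protocol 4.6.1 provides for changes in antihypertensive medication. The stopping proportion is unknown. This stands.

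**The events stay visible.** SAP 5.2.4 repeats the secondary analyses in the other of ITT and FAS, and SAP 13.3 tabulates the same blood-pressure thresholds in all dosed subjects. The test is also last of twelve in the fixed sequence. All true, and it limits the damage, but under SAP 12.3 none of those displays decides.

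**Stronger readings that fail.** A reader might infer that exclusion alone carries the result across 1.3. That compares a point estimate with a rule written for the upper bound. A reader might also extend the point to mean arterial pressure, the other test with a margin. Its window is Weeks 20 to 28, where subjects who stopped before Week 12 have no on-treatment values in any set, so it is barely affected.

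**Conclusion.** The point holds as two text conflicts with one conditional consequence. The PPS minimum is 12 weeks in the protocol and 8 in the SAP, without a flag. SAP 12.3 contradicts SAP 5.2.4 and the protocol on which set is primary. Both are certain from the text.

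The consequence needs three things: SAP 12.3 is followed, worsened hypertension is commoner early on roxadustat, and it leads to stopping before the cut-off. The hazard ratio is then pulled toward 1, more under 12 weeks than under 8, and a false non-inferiority claim becomes more likely. With equal early hazards and equal stopping in both arms there is no bias, so it would be wrong to say that the rule always favours non-inferiority.

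The size cannot be computed from the documents. In the assumed scenarios with 50% stopping, the hazard ratio drops by 0.05 to 0.12 under 8 weeks (1.27 to 1.22; 1.55 to 1.43) and by 0.09 to 0.20 under 12 weeks (1.27 to 1.18; 1.55 to 1.35). None of these changes the decision. Among the cases examined, the upper bound came down to 1.3 or just below only when every subject with an early event stopped under the 12-week rule.

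**What to change.** In SAP 12.3, make ITT (US) or FAS (Ex-US) the deciding set for non-inferiority on worsened hypertension, as SAP 5.2.4 and the protocol already imply. Keep the PPS as supportive, and require the two results to be consistent before non-inferiority is claimed. Amend the sentence on the role of the PPS in SAP 5.2.4 so that it agrees.

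State one PPS minimum duration in both documents. Alternatively, keep 8 weeks in the SAP and record it there as a justified change from the protocol. Either must be done before unblinding. Once the PPS no longer decides the test, the choice between 8 and 12 weeks matters much less.

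The cost is SAP wording; the ITT and FAS runs of the secondary endpoints are already planned in SAP 5.2.4. The small downside is that the hypertension estimate may be less favourable than it would be in the PPS.

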	
Secondary endpoints will be tested using a fixed sequence procedure to adjust for multiple endpoints compared between the pooled roxadustat group vs. pooled placebo, followed by roxadustat TIW vs. pooled placebo. If a null hypothesis is rejected, the claim of roxadustat over placebo will be declared successful and the test will progress to the next comparison in sequence.
 
The secondary endpoints of Hb maintenance will be analyzed using the MMRM model with baseline Hb as covariate and other randomization stratification factors as fixed effects. Missing values will be handled with the MMRM model. The test for these endpoints will compare the pooled roxadustat group (TIW+BIW+QW) to pooled placebo, followed by roxadustat TIW to pooled placebo in a fixed sequence procedure. Separately, pairwise comparisons of roxadustat (2A, 1A) to pooled placebo (1P+2P+3P) will also be performed as exploratory analyses of the BIW and QW maintenance dosing frequencies (from the original and amendment 1 versions of the protocol).
 
The secondary analyses of mean CFB in LDL cholesterol, SF-36 PF subscore, SF-36 Vitality, and MAP will use MMRM models using baseline value as covariate and randomization stratification factors as fixed effects.
 
Time to (and proportion of subjects with) protocol-defined worsened hypertension for the roxadustat group versus pooled placebo will be analyzed using the Cox Proportional Hazards model stratified by the randomization stratification factors. A hazard ratio and its associated 95% confidence interval (CI) will be computed to compare between the roxadustat TIW treatment group and pooled placebo. Noninferiority will be declared if the upper bound of the 2-sided 95% CI of the hazard ratio does not exceed 1.3, superiority will be declared if the upper bound of the 2-sided 95% CI of the hazard ratio does not exceed 1.
 
Time to (and proportion of subjects with) rescue therapy over the first 24 and 52 weeks of treatment will be analyzed using the same method as outlined above.
 
All subjects who have received any dose of study treatment will be included in the safety analyses. Safety parameters including AEs, laboratory parameters, vital signs, and ECG parameters will be tabulated using descriptive statistics. The analytical methods for the composite safety endpoints of interest will be described in a region-specific pooled SAP to reflect the nature of the pooling of these endpoints across multiple studies in the Phase 3 program and the region-specific safety endpoints.

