9.4.3.2 Secondary Efficacy Analyses

The secondary efficacy endpoints will be analyzed using the ITT population as the primary analysis population and PPS population as a supportive analysis population.

A Mixed Model of Repeated Measures will be used to compare the roxadustat and pooled placebo groups in a fixed sequence procedure. Secondary endpoints will be tested using a fixed sequence approach to adjust for multiple endpoints comparing between the pooled roxadustat vs. pooled placebo, followed by roxadustat TIW vs. pooled placebo. If a null hypothesis is rejected, the claim of roxadustat over placebo will be declared successful and the test will progress to the next comparison in sequence.

1. Ex-US only: Mean CFB in Hb averaged over 8 weeks of treatment at Weeks 28 to 36, without rescue therapy within 6 weeks prior to and during this 8-week evaluation period for the 2 treatment groups (in a fixed sequence of pooled roxadustat vs. pooled placebo, followed by roxadustat TIW vs pooled placebo) will be compared using an MMRM model with baseline Hb and eGFR as covariates and treatment group, visit, treatment*visit, and the other randomization stratification factors as fixed effects. The test for this endpoint will compare the roxadustat group to pooled placebo. Separately, as an exploratory analysis to assess the effect of the QW and BIW maintenance dosing frequencies, pairwise comparisons of roxadustat BIW and QW (from the original and amendment 1 versions of the protocol) to pooled placebo (1P+2P+3P) will also be performed.
2. Mean CFB in LDL cholesterol averaged over Weeks 12 to 28 for the 2 treatment groups (pooled roxadustat vs pooled placebo) will be compared using MMRM models with baseline value as covariate and stratification factors as fixed effects.
3. Mean CFB in the SF-36 PF subscore averaged over Weeks 12 to 28 in the ITT subjects with baseline PF subscore below 35 for the 2 treatment groups will be compared using an MMRM model as outlined above .
4. Mean CFB in the SF-36 Vitality subscore averaged over Weeks 12 to 28 in the ITT subjects with baseline vitality subscore below 50 for the two treatment groups will be compared using an MMRM model as outlined above.
5. Mean CFB in MAP averaged over Weeks 20 to 28 for the two treatment groups will be compared using an MMRM model as outlined above.

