6. Time to (and proportion of subjects with) protocol defined worsened hypertension for the pooled roxadustat vs pooled placebo will be compared using Cox Proportional Hazards model adjusting for stratification factors. A hazard ratio and its associated 95% CI will be computed between the roxadustat group versus pooled placebo. Noninferiority will be declared if the upper bound of the 2-sided 95% CIs of the odds ratio does not exceed 1.3. Superiority will be declared if the upper bound of the 2-sided 95% CI of the odds ratio does not exceed one. The incidence rate per PEY by treatment group will also be reported.
7. Time to (and proportion of subjects who received) rescue therapy (composite of RBC transfusion, ESA use, and IV iron) over the first 24 and first 52 weeks for the roxadustat TIW group versus pooled placebo will be compared using Cox Proportional Hazards model adjusting for stratification factors. A hazard ratio and its associated 95% CI will be computed between the roxadustat group versus pooled placebo. Superiority will be

declared if the upper bound of the 2-sided 95% CI of the hazard ratio does not exceed one.

Comparisons of the individual treatment arms from the original and Amendment 1 versions of the protocol (ie, BIW, QW) in roxadustat against pooled placebo will be reported descriptively. Subgroup analyses will also be performed for primary and secondary endpoints by sex, age group, etc.

Due to the large amount of visits to include in the model, the unstructured covariance pattern model will be applied first. If the algorithm for unstructured covariance pattern does not converge, then the heterogeneous Toeplitz structure will be used instead. If this second model also does not converge, then the (homogeneous) Toeplitz structure will be tried, and finally compound symmetry as a covariance structure to achieve convergence.

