6. Time to rescue therapy (composite of blood/RBC transfusion, ESA use, and IV iron) in the first 52 weeks of treatment will be compared using Inverse Probability of Censoring Weighted (IPCW) model detailed in Appendix A or Cox Proportional Hazards model as deemed appropriate. The Cox regression model will adjust for baseline Hb, baseline eGFR and other randomization stratification factors. Hazard ratio and its associated 95% CI will be computed between the roxadustat group versus pooled placebo. Superiority will be declared if the upper bound of the 2-sided 95% CI of the hazard ratio does not exceed one. Proportion of subjects who received rescue therapy over the treatment period will be derived using Kaplan-Meier approach.
7. Mean CFB in the SF-36 Vitality subscore averaged over Weeks 12 to 28 for the two treatment groups will be compared using an MMRM model as outlined above. A subgroup of subjects with baseline vitality subscore below 50 will be analyzed as a sensitivity analysis.
8. Progression of CKD measured by rate of change in eGFR over time adjusted by baseline eGFR, censored at chronic dialysis or kidney transplant will be analyzed using random slope and intercept model. Annualized eGFR slope over time is estimated by a random slope and intercept model using all available eGFR values (one baseline and all post-treatment values up to End of Treatment Period or start of chronic dialysis or kidney transplant) adjusted by Baseline Hb, Region, CV history at Baseline and the interaction terms Baseline eGFR by time point and Baseline Hb by time point). All assessments collected after initiation of chronic dialysis or kidney transplant will be excluded from the analysis.
9. Time to blood/RBC transfusion in the first 52 weeks of treatment will be compared using Inverse Probability of Censoring Weighted (IPCW) model detailed in Appendix A or Cox Proportional Hazards model as deemed appropriate. The Cox regression model will adjust for baseline Hb, baseline eGFR and other randomization stratification factors. Hazard ratio and its associated 95% CI will be computed between the roxadustat group versus pooled placebo. Superiority will be declared if the upper bound of the 2-sided 95% CI of the hazard ratio does not exceed one. Proportion of subjects who received blood/RBC transfusion over the treatment period will be derived using Kaplan-Meier approach.

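### Protocol 9.4.3.2 and SAP 12.3 set different fixed sequences for the secondary endpoints and neither says which governs, so some patterns of results give different confirmatory claims

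*Protocol*

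**What the plan says.** **Protocol.** Section 9.4.3.2 states: "Secondary endpoints will be tested using a fixed sequence approach to adjust for multiple endpoints comparing between the pooled roxadustat vs. pooled placebo", followed by TIW against pooled placebo. After a rejection, "the test will progress to the next comparison in sequence". Seven numbered items follow. The last begins "7. Time to (and proportion of subjects who received) rescue therapy (composite of RBC transfusion, ESA use, and IV iron) over the first 24" and also covers 52 weeks. The synopsis states the same rule ("Secondary endpoints will be tested using a fixed sequence procedure to adjust for multiple endpoints compared between the pooled roxadustat group vs. pooled placebo") but gives its endpoints no numbered order.

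**SAP.** Section 12.3 states: "Secondary endpoints will be tested using a fixed sequence approach to adjust for multiple endpoints comparing between pooled roxadustat vs. pooled placebo, unless otherwise specified", with the same condition that testing moves on only after a rejection. Section 5.3 places the primary and secondary endpoints under this approach at alpha 0.05. Twelve numbered items follow. The sixth is "6. Time to rescue therapy (composite of blood/RBC transfusion, ESA use, and IV iron) in the first 52 weeks of treatment" and the last is "12. Time to (and proportion of subjects with) protocol defined worsened hypertension for the pooled roxadustat vs pooled placebo".

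**Link between the two.** Protocol 9.5 says: "Any significant changes to the analyses described in this protocol will be highlighted in the SAP and the Clinical Study Report". SAP 1 describes itself as a more detailed elaboration of the final protocol. The SAP text supplied has no section listing departures from the protocol, and neither document has a precedence statement.

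**The concern.** A fixed sequence controls the familywise error because there is one order, fixed in advance, and each test is allowed only if all earlier ones succeeded. Here two orders are on file, with different content, and they cannot both be followed. Whether rescue therapy, SF-36 PF, eGFR slope or transfusion counts as confirmed can then depend on which document is cited. Reducing the need for rescue is a stated secondary objective, so the ambiguity reaches a substantive claim. It cannot be repaired credibly once treatment codes are known.

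**Working it through.** **1. The two lists side by side**

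| Endpoint | Protocol 9.4.3.2 | SAP 12.3 |
|---|---|---|
| Hb change, Weeks 28-36 (Ex-US only) | 1 | 1 |
| Hb change, Weeks 28-52, CRP > ULN | not listed | 2 |
| Hb >=10 g/dL, Weeks 28-36 | not listed | 3 |
| Hb by maintenance dose frequency | not numbered | 4 |
| LDL | 2 | 5 |
| Rescue, 52 weeks | 7 | 6 |
| Rescue, 24 weeks | 7 | additional (SAP 4.3) |
| SF-36 Vitality | 4 (baseline < 50) | 7 (all subjects) |
| eGFR slope | additional (8.3) | 8 |
| Transfusion, 52 weeks | not listed | 9 |
| SF-36 PF | 3 (baseline < 35) | 10 (all subjects) |
| MAP | 5 (no margin stated) | 11 (margin 5) |
| Worsened hypertension (margin 1.3) | 6 | 12 |

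**2. Running both gates.** Let one test fail and all others succeed. PF and Vitality are treated as failing in whichever population is used.

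| Only failure | Rescue under protocol order | Rescue under SAP order |
|---|---|---|
| Hypertension, MAP, PF or Vitality | not reached | confirmed at 52 weeks |
| CRP subgroup or Hb >=10 g/dL | confirmed | not reached |
| A dose-frequency test, if item 4 gates | confirmed | not reached |
| LDL | not reached | not reached |
| None | confirmed | confirmed |

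**3. How likely is failure at the hypertension step?** The documents give no power figure for the secondary sequence. The nearest stated figure is 90% power for 35 roxadustat against 150 placebo subjects (0.75 g/dL, SD 1.2). The standard error is 1.2 x sqrt(1/35 + 1/150) = 0.225, and Phi(0.75/0.225 - 1.96) is about 0.91, so that figure reproduces.

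Inputs for the hypertension step:
- The limit is 1.3 on a two-sided 95% interval. The synopsis applies it to the hazard ratio, while Protocol 9.4.3.2 and SAP item 12 write odds ratio. The hazard ratio is used here.
- Allocation is 2:1, so p(1-p) = 2/9.
- N runs from 450 to 1200.
- Event rates are an assumption, because none are given.

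Events needed at a true hazard ratio of 1 are (1.96 + z)^2 x 4.5 / (ln 1.3)^2, with (ln 1.3)^2 = 0.0688:
- 80% power: 2.8016^2 x 4.5 / 0.0688 = about 514.
- 90% power: 3.2416^2 x 4.5 / 0.0688 = about 687.

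Power with D events is Phi( sqrt(2D/9) x (ln 1.3 - ln HR) - 1.96 ):

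| Assumed event rate | N=450: D, power at HR 1 (HR 0.9) | N=1200: D, power at HR 1 (HR 0.9) |
|---|---|---|
| 5% | 22.5, 0.09 (0.13) | 60, 0.16 (0.27) |
| 10% | 45, 0.13 (0.21) | 120, 0.27 (0.48) |
| 20% | 90, 0.22 (0.38) | 240, 0.48 (0.77) |
| 30% | 135, 0.30 (0.52) | 360, 0.65 (0.91) |

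**4. Error rate if the order were left open.** If the order were picked after unblinding, and each list met its own first true null with the two tests independent, the chance of at least one false rejection is 1 - 0.95^2 = 0.0975. Counting only errors in one direction, at 0.025 each, it is 1 - 0.975^2 = 0.0494.

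**The case against.** A SAP may change the testing order before unblinding, and Protocol 9.5 foresees this. The SAP list could be read as the later and therefore governing one. The SAP's front pages were not available, so a revision note there cannot be excluded. The primary endpoints are untouched. This stands, and it narrows the defect to a missing precedence statement and an unflagged change in the text supplied.

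Four stronger readings are tempting but not supported.
- A reader might infer that the synopsis fixes the protocol order. It states only the rule; the numbered order is in 9.4.3.2.
- A reader might take the complement of the power figures, 35-87%, as the share of trials in which rescue is lost. Those figures rest on assumed event rates and a hazard ratio of exactly 1, and they are conditional on passing steps 1 to 5. Step 5, MAP, has no margin in the protocol; read as a test of difference, it could stop the sequence before hypertension is reached.
- A reader might infer that the SAP order leaves the path to rescue clear. Item 5, directly ahead of rescue, declares LDL superiority only if the lower bound of roxadustat minus placebo exceeds 0. Read literally, a fall in LDL fails that gate.
- A reader might take 9.75% as the trial's actual error rate. It requires choosing the order after unblinding, which no document permits.

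**Conclusion.** The concern holds in this form: two alpha-controlled sequences with different content and order, no statement of which governs, and no highlighted change in the supplied SAP text. The consequence is conditional. Claims diverge only when an endpoint fails that gates in one list and not in the other, and the divergence runs in both directions.

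Such a failure is realistic. At a true hazard ratio of 1 and assumed event rates of 10-30%, power at the hypertension step alone is 13-30% with 450 subjects and 27-65% with 1200. A true hazard ratio of 0.9 raises these ranges to 21-52% and 48-91%. A familywise error of about 9.75% is a near-worst case, not an expected value. No sample size or primary analysis is affected.

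**What to change.** Before unblinding, declare one governing sequence for each submission. The later SAP 12.3 list is the natural choice, but a single declared order is what matters. Record in the SAP that it supersedes Protocol 8.2 and 9.4.3.2, as Protocol 9.5 requires, and state which endpoints lie outside alpha control, for example 24-week rescue.

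If the SAP list governs, first:
- correct item 5 so that LDL superiority is declared when the upper bound of the 95% interval for roxadustat minus placebo is below 0;
- state whether the dose-frequency tests in item 4 gate item 5;
- state that rescue is tested as pooled roxadustat against pooled placebo, since Protocol 9.4.3.2 item 7 names the TIW group;
- correct item 12, which refers to the approach in item 4 (a dose-frequency comparison), so that it points to the time-to-event method in item 6.

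The cost is wording, with no new data. The downsides are that 24-week rescue loses confirmatory status, LDL moves from second to fifth and PF from third to tenth, and the SF-36 analyses move from low-baseline subgroups to all subjects. Editing the protocol lists themselves, instead of recording the change in the SAP, would need an amendment with IRB/IEC approval (Protocol 13.2).
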